a) Neuropsychiatric tests. We will perform the BDI and NPI at baseline, at the first experimental session, once by telephone call after 24 hours of LFS, and a fourth time at the final experimental session. The score of the BDI will be compared across sessions and a score that rises above 20 will be considered positive for the development of moderate depression. The NPI assesses frequency, change in severity, and caregiver distress over 12 neuropsychiatric domains and we will look for caregiver reports of significant change across these domains.

b) Motor tests. The Unified Parkinson's Disease Rating Scale (UPDRS) will be performed prior to patient's surgery as part of the patient's routine care. We will repeat the scale at the final experimental session to assess changes in motor symptoms after sustained LFS.

c) Changes in cognitive function will also be assessed as described below.

2. Feasibility. Improvement in cognitive function will be measured by three cognitive tests: the Stroop test, the N-Back test, and the verbal fluency test. We will measure reaction time and error rates and look for significant changes across stimulator frequencies. The results from 20 patients will help us determine if a large-scale study of effectiveness is warranted and feasible.

Describe any primary or secondary safety endpoints.

See above.

PROTOCOL TITLE: Safety and feasibility of using low frequency deep brain stimulation of the subthalamic nucleus to improve cognitive performance in patients with Parkinson's disease

12) Procedures Involved

a) Describe and explain the study design.

The study design is a safety and feasibility study. We aim to identify 20 PD patients who will receive bilateral STN DBS as part of their standard care. We plan to measure the safety of LFS in the STN as measured through psychological, cognitive, and motor scales, and compare cognitive performance with low and high frequency STN DBS. We propose that LFS in the theta range will not negatively affect psychiatric symptoms or alter motor symptoms, and will improve performance on tests of executive functioning.

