without stimulation and will complete the BDI. Informers will complete the NPI. Subsequently, the stimulators will be turned on, and each patient will repeat cognitive testing under gamma frequency (~130 Hz) and theta frequency stimulation (~5 Hz). The order of stimulation will be randomized. Stimulation will occur for 5 minutes prior to and continuously throughout each task. Amplitude and pulse width will be set to 3 V and 120 microseconds accordingly (Laxton & Lozano 2013) or as tolerated by the patient, and will remain constant across sessions. We will wait 20 minutes between testing conditions to elicit about 75% of DBS effects (Temperli et al 2003). At the end of the experimental testing session, the stimulator will be turned off or set to LFS in preparation for the second experimental session.

The second on-site experimental testing session will assess the effects of continuous theta stimulation on cognitive function. Patients will repeat cognitive testing after 48 hours of continuous theta stimulation. This second on-site testing session will occur 3-5 days following the first experimental session. Two days prior to the testing session, patients' stimulators will be turned on to the theta frequency stimulation setting and patients will return home and engage in normal activities. After 48 hours they will return to the clinic and repeat cognitive testing with continuous theta frequency stimulation. The UPDRS, NPI, and BDI will also be performed at this time. At the end of the session, their stimulators will be turned off.

We will screen for psychological changes by telephone once during the 2 day stimulation period. The patient will complete the BDI and a relative or caregiver will complete the NPI over the phone.

The structure of the experimental sessions is shown in Figure 2 and Figure 3.

[figure not shown]

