Safety data will include performance on psychological screening tests, cognitive tests, and motor tests. Efficacy data will include performance on cognitive tests. All data will be reviewed by a safety committee as described above. If any patient develops motor effects that are uncomfortable, the study will be halted for that particular subject. Furthermore, if the patient develops worsening psychological effects as measured through psychological screening tools, the study will be halted and the patient will be referred for appropriate care through the departments of Psychiatry and Neurology at UC Davis.

Safety information will be collected at study visits and with a telephone call. It will be saved in the database established for this study.

Safety data for motor effects will be collected prior to the patient's surgery and at the final study visit. Psychological data will be collected prior to DBS placement, at the first study visit, by phone call during the sustained frequency stimulation period, and at the final clinic visit.

The principal investigator and study members will review the data after each clinic visit and telephone contact with the patient. A safety committee will review the data after the first 4 patients, 8 patients, 12 patients, and 20 patients. The committee will include the PI, [name] in addition to [name], [name], and [name]. [name] is a neurologist, co-director of the DBS group, and has participated in multiple clinical trials involving the Parkinson's disease population. [name] is an expert in neurocognitive assessment in Parkinson's disease and has experience in identifying study related neurocognitive effects in clinical trials in dementia.

Data will be analyzed and evaluated in cohorts of 4 patients through the first 12 patients to determine whether subjects remain safe. This means we will evaluate the safety data from the first 4 patients before proceeding with subsequent subjects. We will evaluate data again after a total of 8 patients, 12 patients, and 20 patients.

PROTOCOL TITLE: Safety and feasibility of using low frequency deep brain stimulation of the subthalamic nucleus to improve cognitive performance in patients with Parkinson's disease

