Safety Data Analysis: To examine possible effects on motor symptoms, we will screen for significant changes in the motor section of the UPDRS score after sustained LFS. After each patient is tested, we will calculate individual changes in UPDRS scoring. After the entire patient population is tested, we will use a T-test to determine if there is a significant change the motor section.

We will also examine changes in psychological symptoms using the BDI and NPI. We will examine percentage of people who convert to moderate depression as indicated by a BDI score 20 or higher. We will also look for significant changes in the BDI and NPI across time using ANOVAs.

Changes in cognition will also be analyzed by looking at reaction time and error rates on different cognitive tests as described previously.

- Any conditions that trigger an immediate suspension of the research.

None.

16) Withdrawal of Subjects

Describe anticipated circumstances under which subjects will be withdrawn from the research without their consent.

Patients unable to perform cognitive tests due to effort or altered mental status.

Patients who experience any change in psychological symptoms that is concerning to the patient, caregiver, or test administrator as assessed through psychological screening tools.

Describe any procedures for orderly termination.

The patient is not undergoing any additional procedures, except for stimulation and cognitive testing.

Describe procedures that will be followed when subjects withdraw from the research, including partial withdrawal from procedures with continued data collection.

Patients' data will be recorded, unless specifically asked to be withdrawn

Patients will continue to be followed for medical management

17) Risks to Subjects

Physical Risk:

- There is minimal to no physical risk. Once the patient's stimulation is turned off, the patient's pre-stimulation symptoms will likely return (Temperli et al 2003).
- There is a small chance that changes in affective symptoms including dysphoria, depression, mania, or psychosis may occur (Smeding et al 2006, Strutt et al 2012). Patients will be carefully screened using standardized assessment tools.
- All cognitive and memory tests are designed to be minimally difficult and pose minimal

PROTOCOL TITLE: Safety and feasibility of using low frequency deep brain stimulation of the subthalamic nucleus to improve cognitive performance in patients with Parkinson's disease

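### The tolerated-setting rule and the motor-discomfort halt overlap without being linked, and neither outcome is counted, so the Aim 1 motor result may describe only those who tolerated stimulation

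*Combined protocol and SAP*

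**What the plan says.** The document is a combined protocol and SAP. Five places bear on this point.

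- **Section 12 (Procedures Involved), settings.** "Amplitude and pulse width will be set to 3 V and 120 microseconds", followed after a citation by "or as tolerated by the patient, and will remain constant across sessions". Motor effects are not mentioned. The section gives no direction or limit for a change and does not say that a change is to be recorded. In experimental session 1 stimulation is switched on twice, at about 130 Hz and about 5 Hz, in random order. The 48-hour period at the low frequency comes afterwards.
- **Section 15 (safety monitoring), halting.** "If any patient develops motor effects that are uncomfortable, the study will be halted for that particular subject". No step for adjusting the setting is mentioned.
- **Section 15, motor data.** "Safety data for motor effects will be collected prior to the patient's surgery and at the final study visit". The analysis is: "After the entire patient population is tested, we will use a T-test to determine if there is a significant change the motor section".
- **Section 16 (Withdrawal of Subjects).** Withdrawal without consent covers "Patients unable to perform cognitive tests due to effort or altered mental status" and concerning psychological change. Motor effects are not listed. On data already collected: "Patients' data will be recorded, unless specifically asked to be withdrawn".
- **Section 11 (Study Endpoints).** Safety is measured by neuropsychiatric, motor and cognitive tests. There is no count of changed settings, intolerance or halts. On the purpose of the sample: "The results from 20 patients will help us determine if a large-scale study of effectiveness is warranted and feasible".

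**The concern.** A patient with an uncomfortable motor effect when stimulation is switched on meets both rules. Under section 12 the patient may continue at a tolerated setting. Under section 15 the study is halted for that patient. No sentence ranks the two rules or says how a setting that is not tolerated differs from an effect that is uncomfortable.

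The larger issue is what Aim 1 can report. Whichever rule staff follow, the event is not a planned outcome. If the patient continues at another setting, the analysis plan has no place for that fact. If the patient is halted before the final visit, the post-stimulation UPDRS may never be obtained, and the patient drops out of the only planned group test of motor safety. A patient halted in session 1 because of an effect at the high frequency would also never reach the 48-hour low-frequency period, which is where most of the evidence on low-frequency safety is to be gathered. At stake is whether the trial can say how many patients tolerated stimulation at the stated settings, separately for each frequency.

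**Working it through.** The plan states no tolerability rate, dropout rate or power for this point, so there is no figure to reproduce. The check sets the rules side by side and then illustrates the scale.

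**Step 1. Which events fall under which rule**

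| When the uncomfortable motor effect appears | Section 12 | Section 15 |
|---|---|---|
| First switch-on in session 1 | A tolerated setting is allowed | Halt |
| Second frequency in session 1, first frequency tolerated | Unclear: settings are to stay constant across sessions, and constancy between the two conditions within session 1 is not spelled out | Halt |
| Later, at a setting already fixed (48-hour period or session 2) | No change foreseen | Halt |

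The third row is consistent. The first two are not reconciled. In the second row, the frequency at which the problem surfaces, and so what happens next, can depend on the randomized order.

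**Step 2. What would be captured**

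The UPDRS is scheduled before surgery and at the final visit, so session 1 has no scheduled motor measure. The data files listed in section 14 are group assignment, background information, scans and test results. Amplitude and pulse width are not named. A subject halted before the final visit has no scheduled second UPDRS, and the T-test needs both values.

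**Step 3. Scale, on assumed rates**

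The number of subjects in the stimulation study is 20 (22 enrolled, less 2 who only try the computer test). The intolerance rate p is an assumption.

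Expected number affected = 20p. Probability of at least one = 1 − (1 − p)^20.

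| p | Expected affected | Not affected | P(at least one) |
|---|---|---|---|
| 5% | 1 | 19 | 64% |
| 10% | 2 | 18 | 88% |
| 20% | 4 | 16 | 98.8% |
| 30% | 6 | 14 | 99.9% |

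Exact (Clopper-Pearson) one-sided 95% upper bound for k of 20 = the 0.95 quantile of Beta(k + 1, 20 − k). For k = 0 this reduces to 1 − 0.05^(1/20).

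- 0 of 20: 1 − 0.05^(1/20) = 0.139, or 14%.
- 2 of 20 (10%): 0.283, or 28%.
- 4 of 20 (20%): 0.401, or 40%.
- If 4 subjects leave and only the 16 completers are described, 0 of 16: 1 − 0.05^(1/16) = 0.171, or 17%.

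**Step 4. Precision of the low- versus high-frequency contrast**

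If every affected subject were lost from the contrast, its standard error would grow by the factor sqrt(1/(1 − p)): 1.05 at 10% and 1.12 at 20%. These are upper bounds. Both frequencies are tested in session 1, so a subject halted after that session has already supplied the contrast, and section 16 keeps recorded data unless the patient asks otherwise.

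**The case against.** The strongest reply is that the rules work in sequence: a tolerated setting is chosen first and held, and the halt applies to an effect that develops at that setting. The constancy clause in section 12 supports this, since it leaves no room for later adjustment. This stands for effects that arise once a setting is fixed. It does not settle an effect at first switch-on, because section 15 has no such limit, nor one that first appears at the second frequency in session 1.

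A reader might infer that the two sections flatly contradict each other, or that section 12 lowers the setting for motor discomfort. The text supports neither: section 12 names no motor effect and no direction of change.

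A reader might also infer that intolerance would leave no trace, or that the trial would report zero. Section 15 says safety information is gathered at visits and by telephone and saved in the database. The investigators review it after each contact, and a committee reviews it after 4, 8, 12 and 20 patients. What is missing is a stated requirement to record these events and a planned count of them. Zero is the worst case.

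A changed setting need not bias the frequency contrast either. If the same setting is used at both frequencies, the within-patient comparison is preserved. Finally, section 7 states that the study is not powered for efficacy, so some loss of precision breaches no stated target. The case therefore rests on the safety result and not on the standard error.

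**Conclusion.** The point holds as an unreconciled overlap combined with a missing safety outcome. The overlap is confined to motor effects when stimulation is switched on, including at the second frequency in session 1. Its consequence is that the Aim 1 motor result could describe only subjects who tolerated stimulation, with no planned figure for those who did not.

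The size depends on a rate that the documents do not give. With an assumed 4 of 20 affected, a trial that counts them reports 20% with an upper bound of 40%. One that does not count them could show 0 of 20 with an upper bound of 14%. With 2 of 20 the comparison is 10% (upper bound 28%) against the same 14%. For a phase 1 safety and feasibility study these are materially different messages. Even at an assumed 5% rate, the chance of at least one such patient is 64%. The change should be made. It does not call the design of the frequency comparison into question.

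**What to change.** 1. Reconcile sections 12, 15 and 16 so that one rule covers an uncomfortable motor effect at switch-on, at the second frequency in session 1, and later. Which rule applies is for the clinical team.
2. Whichever rule is kept, record the amplitude and pulse width used at each frequency. Record each change of setting or halt together with the frequency running at the time.
3. In sections 11, 14 and 15, name as an Aim 1 outcome the number of patients with a changed setting or a halt, by low and high frequency, with an exact confidence interval. Report it beside the UPDRS T-test, and state how many subjects lack the final UPDRS for this reason.
4. Optionally, repeat the low- versus high-frequency contrast without patients whose setting was changed. With only a few such patients it would say little.

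The cost is protocol wording, a few fields on the session form and one extra table. No additional patients or visits are needed. The fields should be in place before testing starts, since settings not written down at the session may be hard to recover.

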PROTOCOL TITLE: Safety and feasibility of using low frequency deep brain stimulation of the subthalamic nucleus to improve cognitive performance in patients with Parkinson's disease

1) Protocol Title

a) Safety and feasibility of using low frequency deep brain stimulation of the subthalamic nucleus to improve cognitive performance in patients with Parkinson's disease

b) *Version: December, 14, 2015*

2) Author of Protocol

X UC Davis Researcher:
[name] [name] (principal investigator)
[name] [name]

Researcher from other institution
Private Sponsor
Cooperative Group
Other: _____

3) IRB Review History

NA

4) Objectives

Our objective is to examine the safety and feasibility of using low frequency deep brain stimulation (DBS) to improve cognition in patients with Parkinson's Disease (PD). Although DBS of the subthalamic nucleus (STN) is a FDA-approved operation that is routinely performed in our patients with advanced PD, there is no clear standard for the stimulation frequency one should use to maximize benefits. There are few previously published studies that use low frequency stimulation (LFS) in PD, and furthermore, there are few studies that have examined the effect of DBS on cognition. Therefore, we propose a feasibility study that will provide safety and initial-efficacy data of low frequency DBS on cognition.

To do so, we plan to vary stimulation frequency in patients who are receiving DBS as part of their standard care. With regards to safety, we do not expect adverse outcomes of LFS. A previous group has utilized LFS for cognition in patients with PD and reported no adverse events (Wojtecki et al 2006). However, we will monitor potential safety issues through psychological, cognitive, and motor testing in cohorts of four patients. In that way, any unexpected safety issues or negative effects on performance will be detected prior to testing additional patients.

We propose to test the executive task performance of 20 patients with PD at baseline and following bilateral STN deep brain stimulator placement under no frequency, high frequency, and low frequency conditions. We further propose to

PROTOCOL TITLE: Safety and feasibility of using low frequency deep brain stimulation of the subthalamic nucleus to improve cognitive performance in patients with Parkinson's disease

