examine cognitive function under a variable duration of LFS. We hypothesize that there will be a trend towards improvement in task performance under the LFS setting, measured through reaction time and error rates, and that this improvement will be stable or enhanced with sustained LFS. We hope to utilize these results to inform the design of a larger phase 2 efficacy study. Our specific aims are as follows:

- 1) To monitor the safety of LFS in the STN of patients with PD by examining the psychological, cognitive, and motor consequences of LFS
- 2) To determine the feasibility of utilizing low frequency DBS to improve cognition in patients with PD by examining if there is a trend toward improved executive function with LFS over high frequency stimulation (HFS) and no stimulation settings.
- 3) To further examine feasibility by determining if the differential effects of LFS versus HFS of the STN are long lasting in a small patient group.

At present, DBS stimulators are set at varying stimulation frequencies based on the acute effects of DBS on motor performance, with limited understanding of cognitive consequences. Understanding the effects of different stimulation frequencies on non- motor tasks will help elucidate the mechanism behind cognitive impairment in PD. If our hypotheses are correct it could lead to the development of new treatment plans that involve alternating between low and high frequency stimulator settings to optimize both motor and cognitive domains. Ultimately, focused treatment for cognition may slow the progression from mild cognitive impairment to dementia, improving real world functioning and quality of life.

5) Background

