The protected health information will not be reused or disclosed to any other person or entity, except as required by law, for authorized oversight of the research study, or for other research for which the use of disclosure of PHI for which an authorization or opportunity to agree or object is not required by 45 CFR 164.512. The research could not be practicably conducted without the waiver, and without access and use of the PHI for recruitment.

9) Compensation to the Subjects

Subjects will be compensated \$10 per session. If the patient decides not to participate in further sessions, they will still receive the compensation for the completed sessions. Travel expenses up to \$30 per patient will be provided if needed. The compensation will be in the form of a gift card and will be given at the time of the visit.

PROTOCOL TITLE: Safety and feasibility of using low frequency deep brain stimulation of the subthalamic nucleus to improve cognitive performance in patients with Parkinson's disease

10) Study Timelines

The duration of the study from subject enrollment of the first patient to final data analysis will be approximately two years. Each individual subject will participate in the study for a maximum of 2 months for a total of 3 on-site experimental sessions and one telephone call. The first on-site visit will occur within the month prior to their planned DBS placement surgery, following the pre-operative visit. The second and third on-site visits will occur within the fourth week after the DBS electrode placement surgery, 3-4 days apart. A telephone call will be made 24 hours prior to the third on-site session to obtain additional safety information (Figure 1). Each participant will remain in the study for approximately 2 months from the time of consent. Participation is on a voluntary basis and subjects will reserve the right to withdraw participation in the study at any point of time. We expect the duration to enroll all study subjects will be approximately 2 years based on the number of patients who meet the inclusion and exclusion criteria.

We expect to complete the study by July 2017. The data will be analyzed as individual patients complete the study with further analyses after data collection is complete.

11) Study Endpoints

1. Safety: Safety endpoints will be measured by neuropsychiatric, motor, and cognitive testing:

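### Apart from the final-visit UPDRS, no adverse-event or physical-symptom question is specified under low-frequency stimulation, so brief physical events at home may go unrecorded unless volunteered

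*Combined protocol and SAP*

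**What the plan says.** The first aim in Section 4 (Objectives) is "To monitor the safety of LFS in the STN of patients with PD by examining the psychological, cognitive, and motor consequences of LFS". The same section describes the method, "we will monitor potential safety issues through psychological, cognitive, and motor testing in cohorts of four patients", and its purpose: "any unexpected safety issues or negative effects on performance will be detected prior to testing additional patients". Section 11 (Study Endpoints) keeps to the same means: "Safety endpoints will be measured by neuropsychiatric, motor, and cognitive testing".

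On timing, Section 15 says of motor safety: "Safety data for motor effects will be collected prior to the patient's surgery and at the final study visit". It also says, in general terms, "Safety information will be collected at study visits and with a telephone call", and that this information is saved in the study database. Section 10 (Study Timelines) describes the call similarly: "A telephone call will be made 24 hours prior to the third on-site session to obtain additional safety information". Where Section 12 (Procedures Involved) gives the content of that call, it is psychological: "The patient will complete the BDI and a relative or caregiver will complete the NPI over the phone". The time budget in Section 12 likewise allots the call 20 minutes of psychological screening and nothing else.

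At the final session (E2) the UPDRS, NPI, BDI and cognitive tests are done with LFS still on. Section 15 analyses the motor section of the UPDRS; Section 14 also mentions the overall scale. Neither says whether patients are asked about events since LFS was switched on.

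Section 15 provides for stopping an individual who develops uncomfortable motor effects, for team review after every visit and call, and for safety committee review after 4, 8, 12 and 20 patients.

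**The concern.** Scheduled scales find what they measure, at the time they are given. A patient could fall or freeze on the first evening at home under LFS and be back to the usual state by E2. The BDI, NPI, cognitive tests and E2 motor score could then all look unremarkable. Unless the patient or caregiver raises the event, nothing in the written procedures draws it out, and no event record is named among the stored data files in Section 14.

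Safety of LFS is the first aim, and Section 5 (Background) describes the safety of LFS at this target as unknown, though presumed favourable. The results are also meant to inform a larger study. If patients are not asked, a statement that no physical events occurred rests on silence. The cohort reviews, which are supposed to find unexpected problems before more patients are treated, would rest on the same silence.

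**Working it through.** The plan gives no event rate, stopping boundary or safety sample-size calculation to reproduce. The check is therefore an inventory of what is specified at each contact under LFS, taken from the prose of Sections 11, 12 and 15. Figure 3, which charts the safety measures by contact, is not available in the text reviewed.

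| Contact under LFS | Specified content | Motor measure | Event question specified |
|---|---|---|---|
| E1, LFS block | Cognitive tests (BDI and NPI come earlier, with stimulation off) | No | No |
| Call after about 24 hours of LFS | BDI and NPI | No | No |
| E2, after 48 hours of LFS | Cognitive tests, UPDRS, NPI, BDI | Yes (UPDRS) | No |

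**Counts.** Three LFS contacts per patient × 20 patients = 60. A motor measure is specified at 1 × 20 = 20 of them, and an adverse-event question at 0 × 20 = 0. Section 12 leaves open whether home LFS starts at the end of E1 or at a separate switch-on two days before E2. A separate switch-on precedes home exposure, so it is not counted.

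**Where the exposure lies.**
- E1 LFS block: 5 min lead-in + 30 min testing = 35 min = 0.583 h.
- Home: 48 h.
- E2: up to 70 min = 1.167 h, if LFS stays on throughout the session.
- Total: 0.583 + 48 + 1.167 = 49.75 h. Home share: 48 / 49.75 = 96%.

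The single contact inside that 96% has neither a motor measure nor an event question.

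**What must happen for an event to be lost.** It must be physical, occur under LFS (mainly at home), resolve before E2, and go unmentioned by both patient and caregiver on the call and at E2.

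**Context for the reviews.** With zero events among n patients and complete capture, the exact one-sided 95% upper limit on the event rate is 1 − 0.05^(1/n):
- n = 4: 53%
- n = 8: 31%
- n = 12: 22%
- n = 20: 14%

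These limits reflect sample size alone and do not measure the gap. Without prompting, a count of zero bounds only the rate of volunteered events. How much further the limit on the true rate should move cannot be calculated, because the documents give no share of events that would be volunteered.

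**The case against.** The best case for the plan is that its lists are not closed. Section 15 says that safety information is collected at visits and by telephone, and Section 10 says that the call is for additional safety information. A member of staff could well ask about physical problems. Patient and caregiver are both spoken to about a day into home LFS and again at E2, so a fall on the first evening would soon be followed by a conversation. Section 29 has staff ask permission before each session. Uncomfortable motor effects stop the individual's participation (Section 15), settings may be adjusted for tolerability (Section 12), patients can raise untoward events with the clinical team (Section 24), and they are told to report injury promptly (Section 27). The documents do not name falls, freezing or involuntary movements as expected effects of LFS, and Section 5 cites an earlier LFS study that reported no adverse events.

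Much of this stands, and it makes the gap narrow. At E1 the LFS block lasts about 35 minutes with staff present, so little is likely to be missed there. The E2 UPDRS is a physical assessment under LFS, so it would be wrong to say that none exists.

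It does not close the gap. Where the content of the call is spelled out, it is psychological. The halting rule acts only on effects that staff learn about. The routes in Sections 24 and 27 depend on the patient speaking up, and neither is linked to the study database, the Aim 1 analysis or the committee. The reviews see only what was recorded.

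**Conclusion.** The concern holds in a limited form. Under the plan as written, transient physical events during home LFS that resolve before E2 and are not volunteered may not reach the Aim 1 results or the reviews at 4, 8, 12 and 20 patients. In size, 0 of 60 planned LFS contacts carry a specified event question, 20 of 60 carry a motor measure, and about 96% of LFS time falls between E1 and E2. It should be fixed because it affects the first aim and costs almost nothing, but it invalidates no planned analysis.

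This rests on the written procedures being what staff follow, and on no event question appearing only in the missing figure or in an institutional reporting policy outside these documents.

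A reader might infer three stronger things that the documents do not support:
- **That physical safety goes unmonitored.** Persistent motor effects are assessed at E2, and there are halting and review rules.
- **That staff will not ask on the call.** The text leaves this unspecified and does not exclude it.
- **That a cohort decision would have gone wrong, or that LFS causes such events.** No event rate or capture rate is given from which to argue either.

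**What to change.** Add one open adverse-event question with a brief prompt for falls, freezing, involuntary movements and any other new physical symptom. Put it to the patient and caregiver on the existing 24-hour call and at E2, covering the time since home LFS was switched on, and ask it once at the end of each E1 stimulation block. Record the answers on a log in the study database, include the log in the after-contact and safety committee reviews of Section 15, and add the counts to Section 11 as a descriptive safety endpoint without a test. The halting rule need not change.

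The cost is four short askings per patient at three existing contacts (two at E1, one on the call, one at E2), a few minutes each, plus one form and an amendment. No visit is added. All three LFS contacts would then carry an event question.

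The downside is that some recorded events will reflect underlying Parkinson's disease or surgical recovery and cannot be attributed to LFS. Asking the same question about a stimulation-off period before E1 is optional. It could help interpretation but would not settle cause, because that period always comes first.
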